# **Health Education Model Led by Community Health Volunteers**

**NCT06312462**

**24-August-2025**

## **Study Protocol and Statistical Analysis Plan**

### **Study Design and Sampling**

A repeated cross-sectional design compared the impact of CHVs-led (CBPR-based) health education versus traditional health education on schistosomiasis-related KAP over 12 months (February 2024 - February 2025). The CBPR approach included: (1) Needs assessment using baseline surveys; (2) Co-design of interventions with community stakeholders; (3) Implementation led by trained CHVs; and (4) Mixed-methods evaluation combining infection rates and questionnaires(Figure 1). The process emphasized cultural adaptation, community ownership, and continued improvement to ensure sustainable interventions.

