## **Study design**

Baseline data were collected in February 2024, followed by a six-month intervention period. Post-intervention data were collected in August 2024, and a follow-up survey was conducted in February 2025 to assess the sustainability of the intervention effects. During the survey, face-to-face questionnaires were administered by CHVs to assess students' KAP related to schistosomiasis. Additionally, the research team distributed sterile wide-mouth plastic containers labeled with unique student identification numbers for morning urine sample collection. Each student provided approximately 30–50 mL of urine under teacher supervision to ensure proper collection procedures. The questionnaires, translated into Kiswahili, were pre-tested and validated. The questionnaire covered KAP of schistosomiasis transmission, exposure, and prevention. And include a survey on students' satisfaction with CHVs in the second questionnaire.

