## Statistical analysis

The data were double-entered into Microsoft Excel, systematically organized, coded, and verified for accuracy before being imported into IBM SPSS Statistics 26.0 for analysis. *S. haematobium* egg counts were stratified into light intensity (1–49 eggs/10 ml of urine) or heavy-intensity ( $\geq 50$  eggs/10 ml of urine) infection, based on WHO guidelines . For the KAP questionnaire: Knowledge scores were calculated based on correct responses (1 point per correct answer, maximum 10 points). Attitudes were evaluated using a 5-point Likert scale with a maximum score of 55 points. Behavioral patterns were scored according to frequency (1-3 points per item), totaling a maximum of 30 points. All scores were converted into percentage equivalents and categorized as "good" (80-100%), "moderate" (60-80%), or "poor" (<60%) . Satisfaction ratings were quantified with 1 point for "dissatisfied," 2 points for "neutral," and 3 points for "satisfied," yielding a maximum satisfaction score of 6 points.

Demographic and KAP data were analyzed descriptively: continuous variables were expressed as Mean  $\pm$  SD (normally distributed) or median [IQR] (non-normal). A two-way repeated-measures ANOVA with Bonferroni correction assessed temporal

effects (baseline/post-intervention/follow-up) and group differences. For ordinal data violating ANOVA assumptions (normality/homoscedasticity via Q-Q plots/Levene's test), the Kruskal-Wallis test was applied.

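### The design is labelled repeated cross-sectional but analysed by repeated-measures ANOVA, linkage of pupils across waves is not stated, and the difference in change between schools is not named as the test of the intervention

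*Combined protocol and SAP*

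**What the plan says.** Study Design and Sampling gives the label: "A repeated cross-sectional design compared the impact of CHVs-led (CBPR-based) health education versus traditional health education". Study design sets three waves: February 2024, August 2024 and February 2025.

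Statistical analysis names the first test, "A two-way repeated-measures ANOVA with Bonferroni correction assessed temporal", and continues with "effects (baseline/post-intervention/follow-up) and group differences". The fallback reads "For ordinal data violating ANOVA assumptions" and, after the assumption checks, "the Kruskal-Wallis test was applied". The same section scores knowledge, attitudes and behaviour numerically, and then: "All scores were converted into percentage equivalents and categorized as" good, moderate or poor. It does not say which of the two forms goes to the fallback, or which groups the fallback compares.

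On linkage, Study design says "During the survey, face-to-face questionnaires were administered by CHVs" and mentions pupil numbers only for urine containers, "labeled with unique student identification numbers for morning urine sample collection". No section says that these numbers were on the questionnaires, kept from wave to wave, or used to match records. Cluster Sampling Implementation enrols every eligible pupil in grades 4 to 6 but does not say whether once or at each wave. Eligibility Criteria excludes pupils with incomplete questionnaires, again without saying whether per wave or overall. Allocation is one intervention school and two control schools, A and B.

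**The concern.** A repeated cross-section draws a sample at each wave and treats the waves as independent. A repeated-measures ANOVA treats wave as a factor within pupil and needs each pupil's scores joined. The document gives the label of one and the model of the other, and does not say how the data were collected in this respect.

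The second issue is which effect answers the question. The aim is to compare two education models and to see whether any gain lasts, so the relevant quantity is the difference in change between schools. A group main effect averages over waves, including baseline, and so picks up any gap that existed before the programme. A wave main effect picks up any rise shared by all schools. The schools were matched on student numbers, gender ratio and age distribution, not on knowledge, attitude or behaviour scores, so a baseline gap is a realistic possibility.

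**Working it through.** The documents give no sample size, SD, within-pupil correlation or effect size, so there is no figure of the plan's to reproduce. Everything below is illustration on assumed inputs: three schools, three waves, normal scores with SD 1, n = 100 or 200 pupils per school, within-pupil correlation ρ = 0.3, 0.5 or 0.7, nominal 5%.

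**1. Which effect is tested, with no intervention effect.** Pupils linked, no school-by-wave variation, 4,000 simulated runs per cell; ranges are over ρ.

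| Test | Assumed situation | n = 100 | n = 200 |
|---|---|---|---|
| ANOVA group main effect | constant 0.3 SD gap in the intervention school | 70-86% | 94-99% |
| ANOVA wave main effect | 0.3 SD rise in all schools | 99-100% | 100% |
| Kruskal-Wallis, schools within one wave | constant 0.3 SD gap | 56-57% | 86% |
| Baseline-to-post contrast, intervention minus pooled controls | both shifts | 4.5-5.3% | 4.8-5.5% |
| Kruskal-Wallis on change scores | both shifts | 4.8-5.6% | 5.2-5.3% |

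Closed-form check of the first row: the noncentrality is n × 0.3² × (2/3) × 3/(1 + 2ρ). At n = 100 this is 18/1.6 = 11.25 for ρ = 0.3 and 18/2.4 = 7.5 for ρ = 0.7, giving 86% and 68%. Check of the third row: (3/π) × n × 0.06 = 5.73 and 11.46, giving 56% and 87%.

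**2. Linked pupils analysed as if unlinked.** The error goes in opposite directions for the two effects.

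- *Change contrast.* Its true variance is 3(1 − ρ)/n, against 3/n assumed. The standard error is overstated by 1/√(1 − ρ) = 1.20, 1.41 and 1.83. Power for a 0.3 SD difference in change falls from 54-88% to 34-41% at n = 100, and from 84-99.5% to 72-82% at n = 200.
- *Group main effect, three schools.* The variance of a school mean over three waves is (1 + 2ρ) times the assumed one. With 2 df the false-positive rate is about exp[−5.99/(2(1 + 2ρ))]: exp(−1.87) = 15%, exp(−1.50) = 22% and exp(−1.25) = 29%. Simulation agrees at about 15-30%.

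**3. School-by-wave variation.** Let s be the SD of random school-by-wave deviations. The linked contrast then rejects with probability 2Φ(−1.96/√(1 + n·s²/(1 − ρ))).

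- s = 0.05: from 9.2% (n = 100, ρ = 0.3: n·s²/(1 − ρ) = 0.36) to 23.0% (n = 200, ρ = 0.7: 1.67). Simulation: 9-24%.
- s = 0.10: from 20.8% (1.43) to 47.9% (6.67). Simulation: 21-46%.
- Kruskal-Wallis on change scores: 12-30% at s = 0.05 and 29-66% at s = 0.10.
- Different pupils at each wave: the contrast rejects in 8-12% and 16-26%.

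So the rates near 5% in step 1 depend on s = 0.

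**The case against.** The strongest reply is that this may be a cohort with the wrong label. Enrolment of all eligible pupils, pupil-level numbers on the containers, the rule of at least two years' residence, the exclusion of temporary pupils and the reference to a second questionnaire all point that way. If so, the ANOVA could be run and only the label is wrong. This is plausible, but none of it states that questionnaires were matched. A reader might infer that the ANOVA could not have been run, or that label and test can never coexist. The documents do not support either: linkage is unstated, and partial overlap of pupils is also possible.

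A second reply is that a two-way repeated-measures ANOVA already contains group by wave. That stands. The gap is that the plan does not make this term the deciding one, so it would go too far to say that the p-values have no identifiable meaning.

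A third is that Kruskal-Wallis on three schools in one wave is a valid test. It is, as a comparison of schools, but it does not test a difference in change. Uses across linked waves would break its independence assumption, but the plan does not state such a use.

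It is also tempting to say that ignoring linkage only wastes precision. Step 2 shows that this is true of the change contrast and false of the group effect, which the plan does name.

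**Conclusion.** The point holds. The design label and the first-named test conflict, nothing in the document resolves the conflict, and the difference in change is not named as the test of the intervention. Reconciling the two sections and naming the tested effect is a must-fix; the fallback and the model details are a should-fix.

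The effect on the results is conditional. On the assumed inputs, a constant 0.3 SD gap without any intervention effect makes the group main effect significant in 70-99% of runs. Linked pupils treated as unlinked give a change contrast that is too conservative and a group effect with about 15-30% false positives. None of these figures measures this study.

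A reader might infer that naming group by wave yields a valid test of the intervention. It does not: any pupil-level test of change, including Kruskal-Wallis on change scores, keeps its 5% level only without school-by-wave variation, and one intervention school gives no means of separating that variation from the effect.

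**What to change.** State whether the same pupils were surveyed at each wave and whether their questionnaires can be linked. Then make Study Design and Sampling agree with Statistical analysis:

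- **Linked:** call it a cohort; use a mixed model with school, wave, school by wave and a pupil random intercept.
- **Different pupils at each wave:** keep the label; use a between-subject school-by-wave model adjusted for grade.
- **Same pupils, no linking ID:** use the between-subject model for the change contrast only, say that its standard error is conservative, and do not test the pooled group main effect.
- **Partial overlap:** use a mixed model with all pupils.

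In each case name the tested effect: change from baseline to August 2024, and to February 2025, in the intervention school minus the mean change in control schools A and B. State how the Bonferroni correction covers the two time points and the three KAP scores. If normality is doubtful, keep the mean-change contrast with robust or bootstrap errors. An ordinal model for the three categories may be added, but as a separate estimand on the log-odds scale.

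Report pupils per school with one, two and three waves, show controls A and B separately, and state that with one intervention school no pupil-level model separates the school effect from the intervention effect.

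Cost: wording in two sections, a check of the questionnaire records and a re-analysis, which in linked form is possible only if linking IDs exist. Precision may look less favourable. The document is dated 24 August 2025, after the last survey, so the change must be labelled as made after data collection, with the tests as now described shown alongside.

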### **Cluster Sampling Implementation**

A three-stage cluster sampling method was implemented:

1. School selection: Three public primary schools were randomly selected from distinct geographical regions of Pemba Island, matched for demographic characteristics (student population, gender ratio, and age distribution).
2. Cluster formation: Within each school, grades 4–6 (ages 8–16 years) were designated as natural clusters, reflecting the target population exposed to schistosomiasis transmission.
3. Participant inclusion: All students meeting eligibility criteria within selected grades were enrolled, minimizing selection bias through complete enumeration within clusters.

Intervention allocation:

- Intervention group: One school received CBPR-based education led by CHVs.

- Control group A and B: Two schools received standard health education from PHCs providers.

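### Only one school received the CHV programme, so the planned group p-values cannot separate the intervention from that school

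*Combined protocol and SAP*

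**What the plan says.** The Cluster Sampling Implementation section describes the selection of schools: "Three public primary schools were randomly selected from distinct geographical regions of Pemba Island". They were matched on student numbers, gender ratio and age distribution. Allocation is then given in two lines: "Intervention group: One school received CBPR-based education led by CHVs" and "Control group A and B: Two schools received standard health education from PHCs providers". Selection was random, but nothing says that the programme was assigned to a school at random.

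The aim in Study Design and Sampling is comparative: "A repeated cross-sectional design compared the impact of CHVs-led (CBPR-based) health education versus traditional health education".

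The Statistical analysis section scores each student and then gives the main test: "A two-way repeated-measures ANOVA with Bonferroni correction assessed temporal" "effects (baseline/post-intervention/follow-up) and group differences". Where the ANOVA assumptions fail, "the Kruskal-Wallis test was applied". The section does not name the unit of analysis or say whether control schools A and B are pooled. It contains no school effect, intraclass correlation, design effect or cluster-robust error, and no statement limiting inference to these three schools.

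**The concern.** Every student taught by CHVs sits in one school in one region. Because scores are assigned per student and no allowance for school is stated, the planned tests are, by inference, student-level tests. There are two ways to code the group factor, and neither isolates the intervention.

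- **A and B pooled.** The standard error reflects variation among students but omits variation among schools. The intervention arm has no second school from which such variation could be seen.
- **Intervention, A and B as three groups.** The factor is then simply school. The overall test can be significant because A differs from B, although both received the same education.

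A comparison of change from baseline is better than a comparison of levels, because stable school differences cancel. School-specific change over the year does not cancel, and with one treated school it cannot be told apart from an intervention effect. At stake is the study's main claim: a significant result could arise from three schools changing differently, with no effect of CHV-led education.

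**Working it through.** The documents contain no sample size, power, alpha or intraclass correlation (ICC), so there is no figure of the plan's own to reproduce.

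**Inputs from the documents:** three schools, one against two; three surveys; student-level scores.

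**Assumptions:** nominal two-sided 5% test, m = 100 to 300 students per school, no true effect, and a range of values for the school-level share of variance.

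**1. Change from baseline to August 2024.** Independent samples at each wave are assumed, following the repeated cross-sectional label; 20,000 simulations for m = 100, 150 and 300.

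- Stable school share 0.05, school-by-time share 0: rejection 4.7, 4.9 and 5.0% with A and B pooled. The baseline does its job here.
- School-by-time share 0.01: 17.1, 21.5 and 32.4% pooled; 22.8, 30.3 and 47.2% with three groups.

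**2. Score levels at a single survey.**

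- Pooled: DE = 1 + (m − 1) × ICC; rejection = 2 × [1 − Φ(1.96/√DE)]. For m = 100 and ICC 0.01, DE = 1.99, 1.96/√1.99 = 1.39, and rejection is 16.5%.
- Three groups: λ = 1 + m × ICC/(1 − ICC); rejection = P(F with 2 and 3(m − 1) df > Fcrit/λ). For m = 100 and ICC 0.01, λ = 2.01, 3.03/2.01 = 1.51, and rejection is 22.4%.

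| ICC | Pooled, m = 100 / 150 / 300 | Three groups, m = 100 / 150 / 300 |
|---|---|---|
| 0.001 | 6 / 7 / 9% | 7 / 7 / 10% |
| 0.01 | 16 / 21 / 33% | 22 / 30 / 47% |
| 0.02 | 26 / 33 / 46% | 37 / 48 / 66% |
| 0.05 | 42 / 50 / 62% | 62 / 71 / 84% |

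The change results at a share of 0.01 agree with the 0.01 row, as expected: the factor 2 from differencing two waves cancels from the inflation.

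**3. Can a school-level analysis rescue the comparison?**

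- One school against two leaves 3 − 2 = 1 degree of freedom, with critical t = 12.706.
- The variance of intervention minus the mean of A and B is 1.5σ², with σ² estimated by (A − B)²/2. The 95% half-width is 12.706 × √1.5 × |A − B|/√2 = 11.0 × |A − B|. The intervention contrast must exceed 11 times the difference between the two controls.
- Power for a 1 SD effect on change uses a noncentral t with SE = √[1.5 × 2 × (s + (1 − s)/m)], where s is the school-by-time share. For s = 0.01 and m = 100, SE = √(3 × 0.0199) = 0.244 and power is 25.2%. Over m = 100, 150 and 300, power is 25.2, 27.5 and 30.6% at s = 0.01, and 20.7, 21.9 and 23.4% at s = 0.02.
- A permutation test over which school was treated has a smallest possible p of 1/3, even had allocation been random.

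The 1-df and 1/3 results need only the one-against-two design. The rejection rates and powers depend on the assumed values.

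**The case against.** The strongest defence has five parts.

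- **The baseline survey.** A change comparison removes stable differences, and with no school-by-time variation it holds its 5% level. This stands. The larger figures in the table apply only to levels. However, the plan refers to temporal effects and group differences without explicitly specifying a group-by-time test, so a comparison of levels cannot be ruled out. Any inflation for change rests on a school-by-time share that the documents do not give.
- **Matching.** It is real and should be credited, but it covers three demographic features. Infection, water exposure and baseline knowledge, attitudes and practice are not listed, and matching does not add a second treated school.
- **Clusters.** The plan says that "grades 4–6 (ages 8–16 years) were designated as natural clusters", so grade might be offered as the cluster. All grades in a school received the same education, so grades do not replicate the intervention.
- **Coding.** Intervention and school coincide literally only under three-group coding. Under pooling, A against B gives 1 degree of freedom of between-school information, though nothing about variation among CHV schools.
- **Bonferroni and the overall test.** Rejections by the three-group test are not all false claims about the intervention, since some come from A against B. The rate for the Bonferroni-corrected intervention contrasts was not calculated. Bonferroni addresses multiplicity, not clustering.

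One gap remains in the figures. Repeated-measures ANOVA suggests students linked across surveys, whereas the change simulation used independent samples. At the same school-by-time share, positive correlation within students would increase the inflation.

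**Conclusion.** The concern holds. The intervention arm is a single unreplicated school, allocation is not described as random, and the planned tests ignore school. Their p-values therefore do not test the intervention, and nothing elsewhere in the document deals with this. That conclusion needs no assumed number.

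The size does depend on assumptions. For a change comparison, the false-positive rate runs from about 5% with no school-by-time variation to about 17–32% (pooled) or 23–47% (three groups) at a share of 0.01 with 100 to 300 students per school. These are scenarios, not estimates for this study. If school-specific change was negligible, the inflation is small, but three schools cannot establish that. The design supports a description of three schools, not a tested causal claim.

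**What to change.** In the Statistical analysis section:

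- State that the school is the unit of allocation, that random allocation is not claimed, and whether A and B are pooled or kept separate.
- State that student-level p-values are not a test of the intervention.
- Tabulate each school's change from baseline to August 2024 and to February 2025, with three contrasts in change: intervention minus A, intervention minus B, and A minus B. If the planned Bonferroni comparisons already produce these, present them as descriptive estimates.
- Treat A minus B only as a rough guide to ordinary between-school variation, since it is one difference between two schools in different regions.
- Do not present a 1-df school-level test as confirmatory. A mixed model or cluster adjustment would not repair the lack of a second treated school.

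The study report should word its conclusion as a non-randomised, descriptive comparison of three schools.

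The cost is wording and one table from data already collected, with no new schools. The headline comparison loses its nominal significance, and no re-analysis of three schools restores a usable confirmatory test. That would take a future study with several schools per arm.

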## **Eligibility Criteria**

- Inclusion:
  - (1) Grades 4 – 6 students aged 8 – 16.
  - (2) Written parental/guardian consent and student assent.
  - (3) Permanent residency in the school's catchment area for  $\geq 2$  years.
- Exclusion:
  - (1) Severe cognitive or communication impairments affecting questionnaire completion.
  - (2) Temporary enrollment (e.g., visiting students).
  - (3) Missing consent documentation or incomplete questionnaires.

## **Study design**

Baseline data were collected in February 2024, followed by a six-month intervention period. Post-intervention data were collected in August 2024, and a follow-up survey was conducted in February 2025 to assess the sustainability of the intervention effects. During the survey, face-to-face questionnaires were administered by CHVs to assess students' KAP related to schistosomiasis. Additionally, the research team distributed sterile wide-mouth plastic containers labeled with unique student identification numbers for morning urine sample collection. Each student provided approximately 30–50 mL of urine under teacher supervision to ensure proper collection procedures. The questionnaires, translated into Kiswahili, were pre-tested and validated. The questionnaire covered KAP of schistosomiasis transmission, exposure, and prevention. And include a survey on students' satisfaction with CHVs in the second questionnaire.

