### Structured health education sessions

The 6-month intervention (February-August 2024) featured (Table 1):

Table 1 CBPR-Integrated Schistosomiasis structured health education sessions.

Session	Core Content	CEPEM Components	Duration	Framework Alignment
1	
Schistosomiasis life cycle & transmission
 
 
• Using local water source photos
 
• Analyzing common exposure behaviors (laundry, farming)
 
	
Community Embedding
 
 
• Culturally-grounded case studies
 
• Trust capital utilization
 
	2 hours	CHVs as Cultural Insiders

---

	Microscopic			
	observation of host			
	snails			
2	• Local snail specimens	Participatory Methodology	2.5 hours	Interactive Sessions
	• High-risk	• Hands-on learning		
	transmission zone			
	identification			
	Pathological impacts			
	on organs	Systems		
3	• Anatomical model demonstration	Reinforcement		Household-
	• Symptom self-check	• Household practice extension	2 hours	School Linkage
	forms			
	Prevention knowledge			
	games	Participatory		
4	• Schistosomiasis quiz	Methodology	1.5 hours	Peer-Led
	• Risk behavior simulation	• Peer-facilitated learning		Learning
	Preventive measures			
	poster exhibition	Systems		
5	• Safe water source guidelines	Reinforcement		Infrastructure
	• Hygiene practice visualization	• Infrastructure advocacy	2 hours	Advocacy
	Key message reinforcement	Community		
6	• Educational booklet distribution	Embedding		Trust Capital
		• Community	1 hours	Utilization
		resource mobilization		

---

---

- Core knowledge

- retention test

---

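### The plan does not define who was surveyed in February 2025; if grades 4–6 were re-sampled, promotion brings in pupils from outside the 2024 enrolled grades and can attenuate the sustainability contrast.

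*Combined protocol and SAP*

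**What the plan says.** All references are to the combined protocol and SAP.

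- **Design** (*Study Design and Sampling*): "A repeated cross-sectional design compared the impact" of the two forms of health education over 12 months.
- **Population** (*Cluster Sampling Implementation*): "grades 4–6 (ages 8–16 years) were designated as natural clusters", and "All students meeting eligibility criteria within selected grades were enrolled". *Eligibility Criteria* repeats the rule as "Grades 4 – 6 students aged 8 – 16". Neither section gives the date on which grade is judged, or says whether enrolment happened once or at each wave.
- **Timing**: *Study design* states "Baseline data were collected in February 2024, followed by a six-month intervention period". *Structured health education sessions* agrees: "The 6-month intervention (February-August 2024) featured" the six sessions of Table 1. The last wave is described as "a follow-up survey was conducted in February 2025", and its stated purpose is to see whether the effects last. No grades are named for it.
- **Analysis** (*Statistical analysis*): a two-way repeated-measures ANOVA covers baseline, post-intervention and follow-up.
- **Identification** (*Study design*): student identification numbers are mentioned as labels on the urine containers. Linking pupils across waves is not mentioned.

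**The concern.** A repeated cross-section normally samples the defined population afresh at each wave, and here grade and age define that population. Two surveys 12 months apart straddle one annual promotion. A fresh February 2025 sample of grades 4–6 would therefore include a grade that was below the enrolled range when the teaching took place.

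The February 2025 wave is the plan's only evidence on durability. If it mixes taught and untaught pupils, an effect that lasted in full in the taught pupils would look as if it had partly faded. The plan neither mentions this nor handles it. Its two descriptions of the data, repeated cross-section and repeated measures, imply different follow-up populations.

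**Working it through.** The plan gives no sample size, grade sizes, effect size or dilution figure, so there is nothing to reproduce. The check has four steps.

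**1. Who is in each grade.** Assume annual promotion and set repeaters aside.

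| Grade, Feb 2024 | Grade, Feb 2025 | In the enrolled grades in 2024? | In a fresh grade 4–6 sample in Feb 2025? |
|---|---|---|---|
| 3 | 4 | No | Yes |
| 4 | 5 | Yes | Yes |
| 5 | 6 | Yes | Yes |
| 6 | above 6 | Yes | No |

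The first row is the source of dilution. The last row changes the grade and age mix, and matters only if the effect differs by grade.

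**2. Size of the attenuation.** Let g be the grade 4 share of the February 2025 sample, r the share of that grade already taught in 2024 (repeaters), and s the effect reaching untaught pupils as a fraction of the full effect (spillover). Assume promotion after August 2024. Then

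share of effect lost = g × (1 − r) × (1 − s).

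All values of g, r and s below are assumptions.

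| Grade sizes 4 : 5 : 6 | g | r = 0, s = 0 | r = 0.10, s = 0.50 |
|---|---|---|---|
| 1 : 1 : 1 | 1/3 = 0.333 | 33% | 0.333 × 0.9 × 0.5 = 15% |
| 0.75 : 1 : 1.25 | 0.75/3.00 = 0.25 | 25% | 0.25 × 0.9 × 0.5 = 11% |
| 1.5 : 1 : 0.75 | 1.5/3.25 = 0.462 | 46% | 0.462 × 0.9 × 0.5 = 21% |

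The range is therefore about 11% to 46%. As an illustration only, with equal grades and r = s = 0, a fully sustained 15-point contrast would be estimated as 15 × (1 − 1/3) = 10 points.

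**3. Whether the control schools cancel it.** Let ΔI and ΔC be the sustained changes in taught pupils under the two forms of education. On the same assumptions, the control schools' new grade 4 also missed the 2024 standard education. With a common untaught share u, the contrast is

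(1 − u)ΔI − (1 − u)ΔC = (1 − u)(ΔI − ΔC).

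At u = 1/3 this is two thirds of the true contrast, so the attenuation remains. If the untaught shares differ between schools, the bias has no fixed size.

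**4. The cohort reading.** If the pupils enrolled at baseline were followed, no 2024 grade 3 pupil enters. Then g = 0 and the loss from this source is 0%.

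**The case against.** The strongest reply is that no section says grades 4–6 were surveyed in February 2025. The grade rule can be read as an entry criterion applied once, and the repeated-measures ANOVA points to followed pupils, for whom there is no such dilution. This stands, and it makes the point conditional. It does not clear the plan, because the stated design label points the other way and nothing settles the matter.

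Other replies stand in part:

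- *Grade 3 may have been taught.* Allocation was by school, and the session description does not restrict attendance to grades 4–6. If grade 3 took part, there is no dilution.
- *Spillover and repeaters are plausible.* Table 1 includes household-linked activities, a poster exhibition and booklets. An age span of 8 to 16 over three grades suggests late entry or repetition. Both reduce the loss, which is why a range is given.
- *Promotion may have fallen between February and August 2024.* The new grade 4 could then have been partly taught, and the loss would be smaller.

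A reader might also infer four stronger things that the documents do not support:

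- That the grade rule would remove the former grade 6 even from a cohort. An entry criterion met at enrolment does not expel a pupil on promotion.
- That losing the taught grade 6 is itself dilution. It changes the mix of pupils.
- That the control schools have no taught/untaught difference. They received standard education, so on the same logic their new grade 4 missed it too.
- That restricting follow-up to grades 5–6 raises the z statistic by a calculable 22%. That figure treats pupils as independent, whereas the comparison rests on one intervention and two control schools, and variation between schools does not shrink with pupil numbers.

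**Conclusion.** The concern holds in conditional form. The follow-up population is undefined, and the design label and the planned analysis imply different ones. If grades 4–6 were re-sampled and the 2024 grade 3 was untaught, the sustained-effect contrast is biased towards apparent decay. The loss is about one third with equal grades, no repeaters, no spillover and promotion after August 2024. Varying grade size, repeaters and spillover gives roughly 11–46%. If the baseline pupils were followed, the loss from this source is zero.

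A reader might infer that the sustainability estimate is in fact diluted by a third. The documents do not support that: they name no grades for February 2025, give no grade sizes or promotion date, and do not say whether grade 3 was taught. What they do show is that nothing in the plan prevents or detects the problem.

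**What to change.** 1. State which grades and pupils each wave covered, when promotion takes place, and whether grade 3 attended any 2024 sessions. Give counts by grade, school and wave.
2. Define the sustainability analysis population as pupils enrolled at baseline, linked by student identification number where the questionnaires carry it.
3. Where linkage is not possible, compare February 2025 grades 5–6 with grades 4–5 at the two 2024 waves, in all three schools. If promotion fell before the August 2024 survey, shift the grade mapping for that wave. Using all three schools matters because the followed pupils are a year older, and only the between-group contrast of changes can allow for that.
4. Report the new grade 4 separately as entrants, outside the sustained-effect estimate. This keeps any evidence of spillover.
5. Reconcile the design description with the analysis: a linked cohort fits repeated measures, while separate cross-sections need a model that does not assume the same pupils at each wave.

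The fallback in item 3 needs no new data and no linkage. Its cost is about a third fewer follow-up records in this contrast with equal grades, and the 2024 grade 6 also drops out of the comparison. Linkage additionally depends on identifiers having been recorded on the questionnaires and kept the same across waves, which the plan does not confirm.
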